### **Human Subjects Protection**

#### **Subject Recruitment Methods**

#### **Informed Consent**

Signed informed consent will be obtained from each subject. One of the two investigators will obtain informed consent. Patients will be contacted by telephone the day before their procedure is scheduled to discuss the general description of the study and the possibility of study inclusion. Full written consent, after answering questions, will have to be performed in the holding room prior to the procedure since most patients will have their pre-procedure examination performed in the holding room and will not be seen prior to the day of surgery.

#### **Confidentiality and Privacy**

Confidentiality will be protected by collecting only information needed to assess study outcomes, minimizing to the fullest extent possible the collection of any information that could directly identify subjects, and maintaining all study information in a secure manner. To help ensure subject privacy and confidentiality, only a unique study identifier will appear on the data collection form. Any collected patient identifying information corresponding to the unique study identifier will be maintained on a linkage file, store separately from the data. The linkage file will be kept secure, with access limited to designated study personnel. Following conclusion of data collection, subject-identifying information will be destroyed *three years after closure of the study by secure shredding*, consistent with data validation and study design, producing an anonymous analytical data set. Data access will be limited to study staff. Data and records will be kept locked and secured, with any computer data password protected. No reference to any individual participant will appear in reports, presentations, or publications that may arise from the study.

#### **Data and Safety Monitoring**

The principal investigator will be responsible for the overall monitoring of the data and safety of study participants. The principal investigator will be assisted by other members of the study staff.

#### **Reporting of Unanticipated Problems, Adverse Events or Deviations**

Any unanticipated problems, serious and unexpected adverse events, deviations or protocol changes will be promptly reported by the principal investigator or designated member of the research team to the IRB.

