### **Objectives**

We expect that tourniquet lidocaine will be superior to straight non-tourniquet lidocaine in reducing propofol injection pain. We also want to determine the association of tourniquet duration on reduction of pain with propofol administration. Small studies indicate that 60 seconds of tourniquet lidocaine is superior to 30 seconds or less of tourniquet duration or mixed lidocaine/propofol for injection. We suspect many clinicians do not use the 60-second tourniquet technique due to the extra time involved but hypothesize that a more practical application by applying the tourniquet as soon as the patient is positioned on the operating table will not only be more widely adopted by clinicians as it does not cause delay but also provide the necessary amount of time for benefit from the tourniquet. We plan to record the time from tourniquet application to start of propofol administration, which we predict will be at least 60 seconds, and see if there is a correlation between duration of venous stasis of IV lidocaine and pain benefit.

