### **Subjects selection criteria • Inclusion Criteria**

Any patient aged  $\geq 18$  years scheduled to receive propofol as part of their sedation or anesthetic.

- **Exclusion Criteria**

Since children (age < 18 years) frequently receive induction of anesthesia by mask, they will be excluded.

Any patient receiving pre-medications prior to their sedation that could alter their recall or perception of the pain such as fentanyl or midazolam.

- **Sample Size**

We estimate that 25 subjects in each of the two groups will be required to test the hypothesis based on prior studies.

**Interventions and Interactions** •

There will be two groups: ○ Group 1: 50mg of 2% lidocaine given just prior to the propofol dose through the IV line.

○ Group 2: 50mg of 2% lidocaine given IV with venous occlusion applied when the patient is positioned on the operating room table and timed until the onset of propofol administration. The tourniquet will either be a latex free tourniquet or McKesson Quick Release tourniquet applied to the forearm 10cm distal to the elbow joint in the tourniquet group. Venous stasis will be confirmed with cessation of flow from hanging IV fluid.

- For both groups, no premedication shall be given, which is the normal practice for these procedures. Study procedures will involve a 20 gauge intravenous (IV) catheter placed in a vein distal to the mid forearm. Venous occlusion will be achieved by either a latex free tourniquet or McKesson Quick Release tourniquet applied to the forearm 10cm distal to the elbow joint. Tourniquet pressure will be somewhat variable but sufficient to cause venous stasis as confirmed by no flow of hanging IV fluid. Injections will be delivered at roughly 1 ml/sec.
- For studies involving interactions the survey, questionnaire or method of observation should be described.
  - Please see Data Collection Form Attached

- The time required should occur within their usual anesthetic parameters and should not delay their procedure nor increase the duration of anesthesia significantly.

- Table illustrating the schedule of events in the study:

Day prior to the procedure	Describe study to the patient by telephone
Day of procedure: holding area	Consent patient for
Day of procedure: holding area	Randomly assign patient to one of two groups

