**Outcome Measures**

1. Self-described discomfort level using 4-point verbal pain scale (None, mild, moderate, severe)

2. Observer-graded discomfort level (Nonverbal vocal complaints, verbal vocal complaints, facial grimace/winces, and restlessness/withdrawal)
3. Post-procedure recall of discomfort using 4-point verbal pain scale (same as #1)

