**Appendix**

**Intravenous Lidocaine to Reduce Propofol Injection Pain:  
A Comparison of Two Methods**

MRN: \_\_\_\_\_

Date: \_\_\_\_\_

Observer: \_\_\_\_\_

PMH:	Chronic Pain Syndrome:	Y/N
	Daily use of Opioids:	
Y/ N		

Group (check one):             A (no tourniquet)             B (tourniquet)

Self-described discomfort level during injection using 4-point verbal pain scale:

- None
- Mild
- Moderate
- Severe

Investigator Assessments:

1) Induction Discomfort Scale (during injection and within 5 seconds after injection)

Grimace

IV forearm withdrawal

Moaning

Verbal statement of discomfort (“it hurts”, etc.)

2) Post-Procedure Discomfort Scale (in Recovery Area just prior to discharge).

I recall \_\_\_\_\_ discomfort in my IV arm while I went to sleep:

No

Mild

Moderate

Severe

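### The plan has no per-patient collection of harms, so non-serious effects of the tourniquet in Group 2 would not be systematically or separately recorded

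*Combined protocol and SAP*

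**What the plan says.** **Safety text.** The section Reporting of Unanticipated Problems, Adverse Events or Deviations states: "Any unanticipated problems, serious and unexpected adverse events, deviations or protocol changes will be promptly reported". The recipient is the IRB. Data and Safety Monitoring states: "The principal investigator will be responsible for the overall monitoring of the data and safety of study participants". Neither section lists events, time points or a way of asking.

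**Outcomes.** Outcome Measures names three discomfort scores: a self-rating, an observer grading and a recalled rating. The second reads "Observer-graded discomfort level (Nonverbal vocal complaints, verbal vocal complaints, facial grimace/winces, and restlessness/withdrawal". No harm outcome is listed.

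**Form (Appendix).** The patient's rating is headed "Self-described discomfort level during injection using 4-point verbal pain scale". The observer's four signs are headed "Induction Discomfort Scale (during injection and within 5 seconds after injection". A recall item, completed in recovery shortly before discharge, asks about discomfort in the IV arm as the patient fell asleep.

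**Exposure.** In Group 2 the vein is occluded from positioning until propofol starts (Interventions and Interactions), a period that Objectives predicts will last 60 seconds or longer. On the force applied: "Tourniquet pressure will be somewhat variable but sufficient to cause venous stasis as confirmed by no flow of hanging IV fluid". Objectives also expects that the technique "will not only be more widely adopted by clinicians as it does not cause delay".

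**The concern.** The two groups differ by a tight band on the forearm and by lidocaine given into an occluded vein. From that description, the effects to expect are minor ones: discomfort from the band, discomfort on the lidocaine push, swelling, bruising or skin marks, numbness, and infiltration at the IV site. This list is my judgement; the documents do not give one. Such effects are neither serious nor unexpected, so they would ordinarily not trigger an IRB report, and the form does not ask about them.

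The technique's purpose is comfort, and the authors hope it will be widely taken up. A reader of the results will want to know what the band itself costs the patient. If that is not asked in both groups, a report of no adverse events would show only that nobody asked, and the information cannot be recovered at analysis.

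**Working it through.** **Step 1. Where could a minor tourniquet effect be recorded?**

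| Place in the plan | What it can catch | What it cannot do |
|---|---|---|
| IRB reporting rule | Unanticipated problems, serious unexpected events, deviations, protocol changes | Prompt for foreseeable minor effects; give a count by group |
| Principal investigator oversight | Whatever staff happen to notice | Ensure the same question is put to every patient |
| Self-rating on the form | Pain during an injection | Cover the interval before it, or say which injection is meant |
| Observer signs on the form | Signs during the injection and for 5 seconds after | Record an earlier period separately |
| Recovery recall item | Any discomfort in the IV arm around sleep onset | Separate band, lidocaine and propofol; record swelling, bruising, numbness or infiltration |

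No row yields harm data by group.

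**Step 2. The word 'injection'.** Both groups receive lidocaine and then propofol. The form does not say which injection it means. The label 'Induction' and the form's title point to propofol. On that reading the interval before propofol lies outside outcomes 1 and 2. If lidocaine is included, one score mixes two sources of pain. On neither reading is discomfort before propofol separately identified.

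**Step 3. What 25 patients could show.** The plan's one design figure is 25 per group. It cannot be reproduced, because no alpha, power, effect size or event rate is stated; I use it only as the denominator.

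With every Group 2 patient asked and no event seen, the exact upper bound solves (1 − p)^25 = α:

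- one-sided 95%: 1 − 0.05^(1/25) = 11.3%
- upper limit of a two-sided 95% interval: 1 − 0.025^(1/25) = 13.7%

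The chance of seeing at least one event is 1 − (1 − p)^25. The true rates p below are assumed, since the documents give none:

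| Assumed true rate | Chance of at least one event in 25 |
|---|---|
| 1% | 22% |
| 2% | 40% |
| 5% | 72% |
| 10% | 93% |

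Full collection would therefore probably reveal a common effect and would say little about a rare one. Without collection there is no defined numerator, and none of these statements can be made.

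**The case against.** The strongest reply is that the trial asks about propofol injection pain and its outcomes answer that. No section plans a claim that the method is harmless or improves overall comfort, and wider uptake is a hope resting on the absence of delay, not an endpoint. This stands: a superiority result on injection pain would be a correct answer to the stated question.

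Three further limits also stand:

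- A reader might infer that the plan's safety text reaches serious unexpected events alone. It does not stop there: it also covers unanticipated problems and deviations, and the principal investigator has general oversight.
- A reader might infer that band discomfort can never be recorded, or must be scored as none. The documents do not support that. The recall item is worded for the arm rather than for propofol, so it can pick up band discomfort, and the undefined word 'injection' leaves room to score pain on the lidocaine push.
- A reader might infer that the benefit could be cancelled by discomfort moved earlier. The documents give no rate of discomfort before propofol in either group, and both groups receive lidocaine, so no net figure can be derived.

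A practical objection concerns the remedy. A question put to the patient just before propofol could lengthen the gap between lidocaine and propofol in Group 1 and the occlusion time in Group 2. Occlusion time is itself a variable of interest under Objectives. That is a good reason not to ask at that moment.

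None of this supplies the missing items. The opening part and the consent pages were not available for this review; risk wording there would not add fields to the form.

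**Conclusion.** The concern holds in a limited form. The plan has no per-patient harm collection, and foreseeable minor effects of the tourniquet are not systematically or separately recorded. The recall item may include some of that discomfort without identifying its source.

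The comparison of propofol injection pain is not invalidated. What the trial could not support is any statement that the tourniquet method is free of harm or reduces overall discomfort. The size of any hidden effect cannot be estimated from the documents. The most that complete collection could offer, with no events in 25, is an upper bound of 11.3% (one-sided 95%).

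The conclusion rests on the protocol text and the form as published, and on my judgement that the effects listed are foreseeable and minor. The gap is worth closing before enrolment because closing it is cheap and the data cannot be obtained afterwards.

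**What to change.** 1. At the recovery visit already planned, and after the recall item so that it is not influenced, add the same tick boxes in both groups: swelling, bruising or skin marks, numbness, IV infiltration, other. Add one question on IV-arm discomfort before the propofol was given.
2. Have the observer already present mark the four existing signs separately for the period from positioning to the start of propofol, in both groups. No question is put to the patient, so neither the lidocaine-to-propofol interval nor the tourniquet time changes.
3. State on the form that 'injection' in outcomes 1 and 2 means the propofol injection.
4. Report the new items by group, and limit the conclusion to propofol injection pain, presented alongside them.

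IRB reporting and the interventions stay as they are. The cost is a few form lines and one table. Two limits remain: the question about the period before propofol relies on recall after sedation, and 25 patients per group cannot rule out uncommon harms.

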**Appendix**

**Intravenous Lidocaine to Reduce Propofol Injection Pain:  
A Comparison of Two Methods**

MRN: \_\_\_\_\_

Date: \_\_\_\_\_

Observer: \_\_\_\_\_

PMH:	Chronic Pain Syndrome:	Y/N
	Daily use of Opioids:	
Y/ N		

Group (check one):             A (no tourniquet)             B (tourniquet)

Self-described discomfort level during injection using 4-point verbal pain scale:

- None
- Mild
- Moderate
- Severe

Investigator Assessments:

1) Induction Discomfort Scale (during injection and within 5 seconds after injection)

Grimace

IV forearm withdrawal

Moaning

Verbal statement of discomfort (“it hurts”, etc.)

2) Post-Procedure Discomfort Scale (in Recovery Area just prior to discharge).

I recall \_\_\_\_\_ discomfort in my IV arm while I went to sleep:

No

Mild

Moderate

Severe

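### The recovery recall item points to induction but does not name the propofol injection, so tourniquet-group patients could count band discomfort; rewording it is a cheap improvement

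*Combined protocol and SAP*

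**What the plan says.** The Objectives set the target as pain from the propofol injection and expect the tourniquet method to be superior.

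Three measures are listed under Outcome Measures, and the Appendix form carries them out:

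- The patient's own rating in the room is headed "Self-described discomfort level during injection using 4-point verbal pain scale".
- The observer's Induction Discomfort Scale covers the injection and the five seconds after it.
- The third measure is given under Outcome Measures as "Post-procedure recall of discomfort using 4-point verbal pain scale (same as #1"). On the form, in the recovery area shortly before discharge, it becomes a sentence about "discomfort in my IV arm while I went to sleep".

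The groups differ in what happens to that arm. According to Interventions and Interactions, Group 2 has "venous occlusion applied when the patient is positioned on the operating room table and timed until the onset of propofol administration". The Background places the tourniquet on the forearm that carries the IV, and the Objectives predict at least 60 seconds from its application to the start of propofol. Group 1 has no band. The same section also states: "For both groups, no premedication shall be given, which is the normal practice for these procedures".

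**The concern.** The recall item is the only one of the three on the form that does not mention the injection. It asks about the IV arm, and in one group only that arm has just had a second possible source of discomfort. The question is put after the procedure, so the patient has to place a sensation in time from memory. No other item records band discomfort, and the form does not tell the patient to leave it out.

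If some Group 2 patients did count the band, the third outcome would mix injection pain with the discomfort of the technique meant to prevent it. Group 1 cannot contribute such reports. This component could therefore act in one direction only, making the tourniquet look less effective on recalled pain than it is. The risk is a missed effect, not a false one.

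**Working it through.** **Figure in the plan.** Sample Size says "We estimate that 25 subjects in each of the two groups will be required". It gives no significance level, power, event rates or effect size, and it does not name the outcome it serves. The 25 cannot be reproduced, and the point does not depend on doing so.

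**Step 1: compare the anchors.**

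| Measure | When asked | Injection named? | Period covered |
|---|---|---|---|
| Patient's rating in the room | Procedure area | Yes | The injection |
| Observer scale | Procedure area | Yes | The injection and 5 seconds after |
| Recall | Recovery, before discharge | No | While going to sleep |

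**Step 2: compare the periods.** The timed band period runs from positioning to the onset of propofol. The period in the recall item is that of falling asleep which, without premedication, begins with propofol. The two are adjacent. The documents do not say when the band comes off relative to loss of consciousness, so overlap is neither shown nor ruled out.

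**Step 3: direction.** Let p1 and p2 be the proportions in Groups 1 and 2 who would report any recalled injection discomfort, and let d = p1 − p2. Let k be the number of Group 2 patients who would otherwise answer No but report the band instead. With all 25 per group answering:

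- recorded Group 2 proportion = p2 + k/25
- recorded difference = p1 − (p2 + k/25) = d − k/25

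Group 1 has no band, so p1 does not change. The difference can only shrink through this route.

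**Step 4: size per patient.** For k = 1 the shift is 1/25 = 0.04, or 4 percentage points. A Group 2 patient who already recalls injection discomfort shifts an any-versus-none difference by 0. If band discomfort is never more than mild, a moderate-or-severe cut is unaffected.

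**Step 5: what is missing.** The documents give no value for k, no rate of recalled discomfort in either group and no rate of band discomfort. The Analytical Plan does not say whether the recall item will be dichotomised, or where. The total effect therefore cannot be estimated.

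**The case against.** The strongest reply is that the item already has an adequate anchor. It fixes the place and the time, and without premedication, falling asleep means propofol induction. Read literally, it leaves out the timed band period. The item also stands under Investigator Assessments, and the schedule of events has staff revisit the patient in recovery to ask about recall. They could clarify the question, and patients will have heard the study explained by telephone and at consent. Finally, nothing in the documents says that the band hurts. The effect needs the band to be uncomfortable, remembered and assigned to the wrong moment.

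All of this stands, and it limits the point to a possibility. It does not remove it. The form gives staff no script for clarifying the item, the two periods adjoin on the same arm, and the form's other measures show that naming the injection is easy.

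A reader might infer more than the documents support:

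- *The third outcome is biased against the tourniquet.* The direction above belongs to one component. No blinding is described, so a patient's expectations could push the answers the other way, and the net bias is undetermined.
- *The trial loses material power on this outcome.* That would need assumed recall rates, an assumed band-discomfort rate and an any-versus-none cut that the plan does not state for this item. The 25 per group is not linked to it either.
- *The in-room items are equally unclear, because lidocaine is injected too.* The form's title and the Induction Discomfort Scale heading already point to propofol.

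**Conclusion.** The point holds as a minor weakness in wording. The recall item is tied to induction but, unlike the form's other measures, does not name the injection, while only Group 2 has a band on the arm in question. Any band discomfort reported there would count against Group 2 alone and reduce the apparent benefit on the third outcome.

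The total size is unknown. The 4-point shift per affected patient rests on 25 evaluable patients per group and on an any-versus-none comparison, and it applies only to patients who would otherwise answer No. The first two outcomes are less exposed, because the form ties them to the injection.

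This is the lowest level of concern: a cheap improvement, not a fault that threatens the trial.

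**What to change.** Before data collection, keep the recall sentence's opening and its four response options, and replace the closing clause so that it asks about discomfort in the IV arm *when the propofol (sleep medicine) was injected*. Make the matching change to the third item under Outcome Measures. This brings the recall item into line with the objective and with the form's in-room rating.

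If the team wants recalled discomfort from the whole technique, band included, that is a defensible but different question. The protocol should then state it, and the present wording could be broadened to match.

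The cost is a change of wording on a short form, with no added visit, question or analysis. The limitation is that some patients may still be unable to separate the two sensations when asked in recovery.
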